8.1.4 Optimal Medical Therapy (OMT)

All patients regardless of randomization group will receive OMT. Unless there is an absolute contraindication, all patients will receive standard secondary prevention with:

1. Aspirin 75-100 mg po daily
2. Ticagrelor 180 mg loading dose then 90 mg po BID unless contraindicated. DAPT duration is as for Institutional protocols, considering that age ≥ 75 is itself a criterion for high bleeding risk and that guidelines suggest at most 6 months of DAPT in this subset of patients. However, in very high bleeding risk: in patients, namely those with one of the following criteria:
 - Clinical indication for chronic (at least 6 months) or lifelong anticoagulation therapy.
 - History of major bleeding which required medical attention within 12 months of the index procedure.
 - History of stroke (ischemic or hemorrhagic).
 - Renal insufficiency (creatinine ≥ 2.0 mg/dl) or failure (dialysis dependent).
 - Systemic conditions associated with an increased bleeding risk (e.g. hematological disorders, including a history of or current thrombocytopenia defined as a platelet count $< 100,000/\text{mm}^3$, or any known coagulation disorder associated with increased bleeding risk).
 - Anemia with hemoglobin $< 11\text{g/dl}$.
 - PRECISE-DAPT score > 24 .

Antiplatelet agent choice is left to the Physicians' discretion and it is mandatory to reduce DAPT duration to 1 month.

3. An ACE inhibitor or ARB appropriately titrated to target a blood pressure of < 130/85. If the patient continues to experience hypertension with BP > 130/85, additional blood pressure lowering treatments should be added: either a thiazide diuretic or dihydropyridine calcium channel blocker. The goal of antihypertensive therapy is to achieve and maintain a target blood pressure (BP) of < 130/85 mm Hg.
4. Statin therapy: Atorvastatin 40-80 mg daily or rosuvastatin 20-40 mg daily or simvastatin 40 mg daily. If, at any time during follow-up, the LDL cholesterol is above the target of 70 mg/dl, the statin dose should be further maximized (if not already attempted). If this still does not result in the desired effect, then ezetimibe can be added. If a patient has a statin related side effect, then, either a lower dose of the same statin or use of a different statin with or without the addition of ezetimibe can be considered.
5. If the patient is diabetic, the goal is to maintain fasting blood glucose levels between 80-135 mg/dl and hemoglobin A1c levels <7.0%, in accordance with published recommendations of International Guidelines. If these criteria are not met on oral hypoglycemic therapy, then insulin should be strongly considered.
6. If the patient has significant LV dysfunction, consideration should be given to administration of an aldosterone antagonist.

8.1.5 Criteria for revascularization in patients randomized to the culprit only group

1. Hospitalization for recurrent MI (STEMI or NSTEMI).
2. Hospitalization for hemodynamic instability or refractory ischemic heart failure (defined as Killip class ≥ 3).
3. Intractable angina (CCS Class 3 or 4 symptoms) despite optimal medical therapy and positive functional assessment (FFR, iFR, cFFR, QFR) or objective, proven and documented evidence of

ischemia in the territory of one or more vessels (myocardial perfusion scintigraphy with ischemic territory greater than 10% of overall left ventricular mass).

Optimal medical antianginal therapy is considered as per guidelines and suggested by a recent consensus document (44). Nitrates, β -blockers, calcium-channel blockers, Ivabradine and Ranolazine must be all attempted and titrated to the maximum tolerated dose.

Table 1 | Drugs for angina: pharmacology, symptom relief, outcomes benefits, and guideline recommendations

Antianginal drug	HR	SBP	DBP	PVR	CC	CV	Symptom relief	Outcomes benefit	ESC*	ACC/AHA*
Nitrates										
Short-acting	↑	↓↓	↓↓	↓	-	↑↑↑	Yes	No	IB	IB
Long-acting	↑	↓	↓	↓	-	↑↑	Yes	No	IIB	IB
β-Blockers										
Noncardioselective	↓↓↓	↓↓	↓↓	↑	↓↓	-	Yes	No	IA	IB
Cardioselective (preserved EF)	↓↓↓	↓↓	↓↓	-	↓↓	-	Yes	No	IA	IB
Cardioselective (reduced EF)	↓↓↓	↓↓	↓↓	-	↓↓	-	Yes	Yes	IB	IB
With vasodilatation (preserved EF)	↓↓	↓↓↓	↓↓↓	↓↓	↓	-	Yes	No	IB	IB
With vasodilatation (reduced EF)	↓↓	↓↓↓	↓↓↓	↓↓	↓	-	Yes	Yes	IA	IA
Calcium-channel blockers										
Dihydropyridines	↑	↓↓↓	↓↓↓	↓↓↓	↑	↑↑↑	Yes	No	IA	IB
Nondihydropyridines	↓↓	↓↓	↓↓	↓↓	↓↓	↑↑	Yes	No	IA	IIB
Other (considered second-choice treatment in guidelines)										
Ivabradine	↓↓	↓	↓	-	-	-	Yes	No	II _B	NA
Nicorandil	↑	↓↓	↓↓	↓	-	↑↑↑	Yes	Yes	II _B	NA
Ranolazine	-	-	-	-	-	-	Yes	No	II _B	IIA
Trimetazidine	-	-	-	-	-	-	Yes	No	II _B	NA

*Guideline classification of benefit: class I = benefit >>> risk; class II_a = benefit >> risk; class II_b = benefit > risk. Level of evidence: A – one or two large, randomized trials; B – one randomized trial or small meta-analysis. C.C., cardiac contractility; CV, coronary vasodilatation; DBP, diastolic blood pressure; EF, ejection fraction; HR, heart rate; NA, not available; PVR, peripheral vascular resistance; SBP, systolic blood pressure.

[figure not shown]

Figure 5 | Possible combinations of classes of antianginal drugs according to different comorbidities. BB, β -blockers; DHP, dihydropyridine calcium-channel blockers; DILT, diltiazem; IVAB, ivabradine; NIC, nicorandil; NITR, nitrates; Non Sel-BB, nonselective β -blockers; RAN, ranolazine; Sel-BB, β_1 -selective blockers; TRIM, trimetazidine; VER, verapamil.

[figure not shown]

Figure 4 | Possible combinations of classes of antianginal drugs according to different comorbidities. BB, β -blockers; DHP, dihydropyridine calcium-channel blockers; DILT, diltiazem; HR, heart rate; IVAB, ivabradine; NIC, nicorandil; NITR, nitrates; RAN, ranolazine; TRIM, trimetazidine; VER, verapamil.

8.1.6 Index Coronary Angiogram and Functional Assessment

The initial angiogram and PCI for the index CAA and the functional assessment performed in the Functionally-driven arm should be recorded, anonymized and maintained locally for shipment to the angiographic and functional core lab (CD, DVD or digital files are acceptable).

8.1.7 Follow up

After initial hospital discharge, routine clinic follow-up will occur at 1 month \pm 14 days (telephone contact or clinic visit), 1 year (clinic visit) and yearly clinic visits thereafter up to 3 years. At each visit, clinical outcomes (death, MI, stroke, bleeding), compliance with medical therapy and smoking cessation, will be assessed. LDL, blood pressure and glycemic targets, anginal status (SAQ), quality of life (EQ-5D) and physical performance (SPBB) will be assessed at the 12-month and 3 year-follow-up visit.

9 STUDY DEFINITIONS

9.1 Myocardial Infarction (MI)

MI will be defined according to the 4th universal definition of myocardial infarction (45).

Universal definitions of myocardial injury and myocardial infarction
Criteria for myocardial injury
The term myocardial injury should be used when there is evidence of elevated cardiac troponin values (cTn) with at least one value above the 99th percentile upper reference limit (URL). The myocardial injury is considered acute if there is a rise and/or fall of cTn values.
Criteria for acute myocardial infarction (types 1, 2 and 3 MI)

The term acute myocardial infarction should be used when there is acute myocardial injury with clinical evidence of acute myocardial ischaemia and with detection of a rise and/or fall of cTn values with at least one value above the 99th percentile URL and at least one of the following:
 
 • Symptoms of myocardial ischaemia; • New ischaemic ECG changes; • Development of pathological Q waves; • Imaging evidence of new loss of viable myocardium or new regional wall motion abnormality in a pattern consistent with an ischaemic aetiology; • Identification of a coronary thrombus by angiography or autopsy (not for types 2 or 3 MIs). 
Post-mortem demonstration of acute athero-thrombosis in the artery supplying the infarcted myocardium meets criteria for type 1 MI. Evidence of an imbalance between myocardial oxygen supply and demand unrelated to acute athero-thrombosis meets criteria for type 2 MI. Cardiac death in patients with symptoms suggestive of myocardial ischaemia and presumed new ischaemic ECG changes before cTn values become available or abnormal meets criteria for type 3 MI.

Criteria for coronary procedure-related myocardial infarction (types 4 and 5 MI)

Percutaneous coronary intervention (PCI) related MI is termed type 4a MI. Coronary artery bypass grafting (CABG) related MI is termed type 5 MI. Coronary procedure-related MI \leq 48 hours after the index procedure is arbitrarily defined by an elevation of cTn values $>$ 5 times for type 4a MI and $>$ 10 times for type 5 MI of the 99th percentile URL in patients with normal baseline values. Patients with elevated pre-procedural cTn values, in whom the pre-procedural cTn level are stable (\leq 20% variation) or falling, must meet the criteria for a $>$ 5 or $>$ 10 fold increase and manifest a change from the baseline value of $>$ 20%. In addition with at least one of the following:
 
 • New ischaemic ECG changes (this criterion is related to type 4a MI only); • Development of new pathological Q waves; • Imaging evidence of loss of viable myocardium that is presumed to be new and in a pattern consistent with an ischaemic aetiology; • Angiographic findings consistent with a procedural flow-limiting complication such as coronary dissection, occlusion of a major epicardial artery or graft, side-branch occlusion-thrombus, disruption of collateral flow or distal embolization. 
Isolated development of new pathological Q waves meets the type 4a MI or type 5 MI criteria with either revascularization procedure if cTn values are elevated and rising but less than the pre-specified thresholds for PCI and CABG. Other types of 4 MI include type 4b MI stent thrombosis and type 4c MI restenosis that both meet type 1 MI criteria. Post-mortem demonstration of a procedure-related thrombus meets the type 4a MI criteria or type 4b MI criteria if associated with a stent.

Criteria for prior or silent/unrecognized myocardial infarction

Any one of the following criteria meets the diagnosis for prior or silent/unrecognized MI:
 
 • Abnormal Q waves with or without symptoms in the absence of non-ischaemic causes. • Imaging evidence of loss of viable myocardium in a pattern consistent with ischaemic aetiology. • Patho-anatomical findings of a prior MI.

©ESC/ACC/AHA/WHF 2018

The leading symptom that initiates the diagnostic and therapeutic cascade in patients with suspected MI is chest pain. Based on the electrocardiogram (ECG), two groups of patients should be differentiated: (1) Patients with acute chest pain and persistent ($>$ 20 min) ST-segment elevation. This condition is termed ST-elevation ACS and generally reflects an acute total coronary occlusion. Most patients will ultimately

[figure not shown]
develop an ST-elevation myocardial infarction (STEMI). The mainstay of treatment in these patients is immediate reperfusion by primary angioplasty or fibrinolytic therapy. (2) Patients with acute chest pain but no persistent ST-segment elevation. ECG changes may include transient ST-segment elevation, persistent or transient ST-segment depression, T-wave inversion, flat T waves or pseudo-normalization of T waves or the ECG may be normal. The clinical spectrum of NSTEMI may range from patients free of symptoms at presentation to individuals with ongoing ischemia, electrical or hemodynamic instability or cardiac arrest. The pathological correlate at the myocardial level is cardiomyocyte necrosis. A small proportion of patients may present with ongoing myocardial ischemia, characterized by one or more of the following: recurrent or ongoing chest pain, marked ST depression on 12-lead ECG, heart failure and hemodynamic or electrical instability. Due to the amount of myocardium in jeopardy and the risk of malignant ventricular arrhythmias, immediate coronary angiography and, if appropriate, revascularization are indicated.

9.1.1 Clinical criteria for MI

The clinical definition of MI denotes the presence of acute myocardial injury detected by abnormal cardiac biomarkers in the setting of evidence of acute myocardial ischaemia.

9.1.2 Criteria for myocardial injury

[figure not shown]
Detection of an elevated cTn value above the 99th percentile URL is defined as myocardial injury. The injury is considered acute if there is a rise and/or fall of cTn values.

Criteria for type 1 MI

Detection of a rise and/or fall of cTn values with at least one value above the 99th percentile URL and with at least one of the following:

[figure not shown]
- Symptoms of acute myocardial ischaemia;
- New ischaemic ECG changes;
- Development of pathological Q waves;
- Imaging evidence of new loss of viable myocardium or new regional wall motion abnormality in a pattern consistent with an ischaemic aetiology;
- Identification of a coronary thrombus by angiography including intracoronary imaging or by autopsy.^a

Criteria for type 2 MI

Detection of a rise and/or fall of cTn values with at least one value above the 99th percentile URL, and evidence of an imbalance between myocardial oxygen supply and demand unrelated to coronary thrombosis, requiring at least one of the following:

- Symptoms of acute myocardial ischaemia;
- New ischaemic ECG changes;
- Development of pathological Q waves;
- Imaging evidence of new loss of viable myocardium or new regional wall motion abnormality in a pattern consistent with an ischaemic aetiology.

Criteria for type 3 MI

Patients who suffer cardiac death, with symptoms suggestive of myocardial ischaemia accompanied by presumed new ischaemic ECG changes or ventricular fibrillation, but die before blood samples for biomarkers can be obtained, or before increases in cardiac biomarkers can be identified, or MI is detected by autopsy examination.

9.2 Death

Deaths will be classified as cardiovascular, non-cardiovascular or undetermined cause according to ARC-2 criteria (43). Deaths of undetermined cause will default to cardiovascular (but will also be reported as a separate subcategory of cardiovascular death to denote this uncertainty). Deaths related to the procedure or complications of the procedure (or concomitant treatment) will be classified as cardiovascular. Within cardiovascular deaths, hemorrhagic deaths will be clearly identified. Only deaths due to a documented non-cardiovascular cause (e.g., cancer) will be classified as non-cardiovascular.

ARC-2 classification of death:

Type of Death	Definition
Cardiovascular death	
Cardiovascular death is defined as death resulting from cardiovascular causes. The following categories may be collected:
 
 1. Death caused by acute MI 2. Death caused by sudden cardiac, including unwitnessed, death 3. Death resulting from heart failure 4. Death caused by stroke 5. Death caused by cardiovascular procedures 6. Death resulting from cardiovascular hemorrhage 7. Death resulting from other cardiovascular cause
Noncardiovascular death	
Noncardiovascular death is defined as any death that is not thought to be the result of a cardiovascular cause. The following categories may be collected:
 
 1. Death resulting from malignancy 2. Death resulting from pulmonary causes 3. Death caused by infection (includes sepsis) 4. Death resulting from gastrointestinal causes 5. Death resulting from accident/trauma 6. Death caused by other noncardiovascular organ failure 7. Death resulting from other noncardiovascular cause
Undetermined	
Undetermined cause of death is defined as a death not attributable to any other category because of the absence of any relevant source documents. Such deaths will be classified as cardiovascular for end point determination.

MI indicates myocardial infarction.

9.3 Ischemia-driven revascularization

Requires the following criteria:

1. Ischemic symptoms consistent with CCS class ≥ 3 angina despite optimal medical therapy

AND

2. PCI or CABG of either the culprit or a non-culprit lesion that lead to enrollment into the trial PLUS at least

ONE of the following:

- A. Positive functional study (Exercise or myocardial perfusion imaging or stress or dobutamine echo)

demonstrating clear evidence of reversible ischemia corresponding to a stenosis in a vessel other than the culprit vessel that lead to enrollment into the trial,

OR

- B. New ischemic ECG changes (ST-segment depression ≥ 1 mm, ST-segment elevation ≥ 1 mm or T wave inversion ≥ 2 mm) at rest or with exertion in a distribution consistent with a stenosis in a vessel other than the culprit vessel that lead to enrollment into the trial,

OR

- C. $FFR \leq 0.80$, $iFR \leq 0.89$, $cFFR \leq 0.85$, $QFR \leq 0.80$ in a lesion in a vessel other than the culprit vessel that lead to enrollment into the trial.

All ischemic-driven revascularizations will be sub-categorized as to whether they were due to the culprit lesion or due to a non-culprit lesion that led to enrollment into the trial.

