5.3 Exploratory endpoints

- To test if a functionally-driven complete revascularization is superior to a culprit only strategy in the reduction of ischemia driven revascularization at 1, 3 and 5 years

[figure not shown]
- To test if non-invasive functional strategy based on QFR evaluation is superior to a culprit only strategy in terms of target lesion failure (TLF) at 1, 3 and 5 years
- To test if functional strategy based on AFI evaluation is superior to a culprit only strategy in terms of target lesion failure (TLF) at 1, 3 and 5 years
- To test if non-invasive functional strategy based on QFR evaluation is superior to a culprit only strategy in terms of ischemia-driven revascularization at 1, 3 and 5 years
- To test if functional strategy based on AFI evaluation is superior to a culprit only strategy in terms of ischemia-driven revascularization at 1, 3 and 5 years
- To test if non-invasive functional evaluation (QFR) is non-inferior to an invasive functional strategy (FFR, iwFR, cFFR) in terms of target lesion failure (TLF) at 1, 3 and 5 years
- To test if functional evaluation with AFI is non-inferior to an invasive functional strategy (FFR, iFR, cFFR) in terms of target lesion failure (TLF) at 1, 3 and 5 years
- To test if non-invasive functional evaluation (QFR) is non-inferior to an invasive functional strategy (FFR, iwFR, cFFR) in terms of ischemia driven revascularization at 1, 3 and 5 years
- To test if functional evaluation AFI is non-inferior to an FFR guided strategy in terms of ischemia driven revascularization at 1, 3 and 5 years
- To test if a functionally-driven complete revascularization is superior to a culprit only strategy in terms of quality of life measured with EQ-5D quality of life scale at 1, 3 and 5 years
- To test if a functionally-driven complete revascularization is superior to a culprit only strategy in terms of physical performance measured with short physical performance battery (SPBB) at 1, 3 and 5 years
- To test if a functionally-driven complete revascularization is superior to a culprit only strategy in terms of angina symptoms control measured with Seattle Angina Questionnaire (SAQ) Frequency scale at 1 year

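### Section 9.3 admits culprit-lesion procedures as ischemia-driven revascularization but accepts proof of ischemia only from outside the culprit vessel

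*Protocol*

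**What the plan says.** Section 9.3 of the protocol builds the definition from two conditions joined by AND.

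- Criterion 1 is symptomatic: "Ischemic symptoms consistent with CCS class ≥ 3 angina despite optimal medical therapy".
- Criterion 2 concerns the procedure, "PCI or CABG of either the culprit or a non-culprit lesion that lead to enrollment into the trial", and needs at least one of A, B or C in addition.

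The three evidence options are restricted by location in the same way:

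- A, a positive functional study, must show "reversible ischemia corresponding to a stenosis in a vessel other than the culprit vessel".
- B, new ECG changes, must appear "at rest or with exertion in a distribution consistent with a stenosis in a vessel other than the culprit vessel".
- C, a positive FFR, iFR, cFFR or QFR, must be found "in a lesion in a vessel other than the culprit vessel that lead to enrollment into the trial".

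The section closes with: "All ischemic-driven revascularizations will be sub-categorized as to whether they were due to the culprit lesion or due to a non-culprit lesion".

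The endpoint is used in section 5.3, first to test superiority of complete revascularization "in the reduction of ischemia driven revascularization at 1, 3 and 5 years".

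**The concern.** Criterion 2 and the closing sentence both expect culprit-lesion events among those counted. The evidence options allow none of these to qualify through ischemia in the culprit's own territory. The two parts of the definition cannot both be applied as intended.

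Section 9.9 has a blinded committee adjudicate revascularizations and makes its decisions final for the analysis. An adjudicator who follows section 9.3 literally must reject a symptomatic culprit-stent restenosis with proven ischemia in its own territory. One who follows the evident purpose of criterion 2 would accept it. The same case could be coded either way, and whichever coding is chosen enters the results.

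**Working it through.** The protocol gives no rate or other figure for this endpoint, so the check is logical: apply the rule as written to each possible case. The rule is criterion 1 AND criterion 2 AND (A or B or C), with A, B and C each requiring evidence outside the culprit vessel.

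| Lesion treated | Where the ischemia evidence lies | Criterion 1 met | Counted? |
|---|---|---|---|
| Culprit lesion | Culprit vessel only | Yes | No |
| Culprit lesion | Another vessel | Yes | Yes, as a culprit event |
| Further lesion in the culprit vessel | Culprit vessel only | Yes | No |
| Lesion in another vessel | That other vessel | Yes | Yes, as a non-culprit event |
| Lesion in another vessel | Culprit vessel only | Yes | No |
| Any | Any | No | No |

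**Row 1** is the plain contradiction. Criterion 2 accepts the procedure and the closing sentence has a category for it, but none of A, B or C can be met.

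**Row 2** is the reverse error. The event counts and is filed under the culprit lesion, although the evidence that qualified it concerns a vessel that was not the one treated.

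**Rows 1 and 2 together** show that no culprit event is ever captured through its own ischemia. This is exact and needs no assumed rate.

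**Row 3** extends row 1 to a second lesion in the culprit vessel. It is a non-culprit lesion, yet it fails for the same reason.

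**Reach.** Section 5.3 uses the endpoint in five objectives:

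1. Complete versus culprit-only, superiority.
2. QFR-based strategy versus culprit-only, superiority.
3. Strategy based on adenosine-free indices versus culprit-only, superiority.
4. QFR versus invasive assessment, non-inferiority.
5. Adenosine-free indices versus FFR, non-inferiority.

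Each is assessed at three times, which gives 5 × 3 = 15 comparisons.

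**Primary endpoint.** Section 5.1 uses any revascularization, so section 9.3 does not enter it. The sample size confirms this. Section 10.1 takes 15% in the control group and a 30% relative reduction, that is 0.15 × 0.70 = 10.5%. With a one-sided 5% level (section 10), 80% power and the usual pooled two-proportion formula:

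n per arm = [1.645 × √(2 × 0.1275 × 0.8725) + 0.842 × √(0.15 × 0.85 + 0.105 × 0.895)]² / 0.045² ≈ 678.2, rounded up to 679.

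The total is 2 × 679 = 1358, as stated. No input comes from section 9.3.

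**The case against.** **It could be a deliberate non-culprit endpoint.** The trial is about non-culprit lesions, so limiting the evidence to other vessels might be intended. If so, criterion 2 and the closing sentence are wrong, because both name the culprit lesion. Where the protocol wants a non-culprit restriction it says so, as in the device-oriented composite in section 5.2. Either way, the text has to be reconciled.

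**The endpoint is exploratory.** This stands. Nothing confirmatory depends on the definition, which limits the weight of the point but does not remove the contradiction.

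**The same-vessel case is narrow.** This also stands. Section 7.1 describes multivessel disease, and the Finkelstein–Schoenfeld strata in section 10 are two or three diseased vessels. Every patient is therefore presumed to have disease elsewhere. A further lesion in the culprit vessel remains possible, but only as an edge case.

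**Stronger readings that the protocol does not support.**

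- A reader might infer that procedures done for MI are excluded. Section 9.3 contains no such exclusion, and it never claims to count them. An MI with symptoms meeting criterion 1 and ECG changes in a non-culprit territory can qualify, since B accepts ST elevation and changes at rest. Section 8.1.5 does list "Hospitalization for recurrent MI (STEMI or NSTEMI" separately from severe angina, but it sets the permitted reasons for revascularization in the culprit-only arm and does not define an endpoint. What remains is that criterion 1, which describes refractory angina, fits acute MI poorly and leaves the handling of such procedures unclear.
- A reader might size the loss from the MI rates tabulated in section 10.1. Those are counts of infarctions in other studies. The protocol gives neither the share leading to revascularization nor the share that would fail criterion 1.
- A reader might infer that the trial loses its objective check on the open-label revascularization component of the primary composite. The protocol gives this endpoint no such role. It relies on restrictive criteria in the culprit-only arm, blinded adjudication, and secondary composites of death or cardiovascular death with MI.

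**Conclusion.** The contradiction within section 9.3 is real and follows from the wording alone. Culprit-vessel events captured through their own ischemia number zero by definition, and the culprit category can hold only events that qualified on evidence from another vessel. Five exploratory objectives, at three times each, rest on this definition.

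How many events would be misclassified cannot be derived, because the protocol gives no rate of culprit-vessel repeat procedures. The culprit lesion is treated before randomization in every patient, so such events can occur in either arm, and the direction of any bias cannot be derived either.

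The primary composite, its power and the sample size are unaffected. The handling of procedures done for MI is a secondary point about clarity. It is not a demonstrated exclusion.

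**What to change.** In A, B and C of section 9.3, replace the restriction to vessels other than the culprit with a reference to *the vessel being revascularized*. Keep the culprit/non-culprit sub-category, which then becomes meaningful. Carry the same wording into the adjudication committee charter.

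If a non-culprit endpoint was intended after all, remove the culprit lesion from criterion 2 and delete the sub-category.

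Add one sentence saying whether a procedure done for an adjudicated MI counts and, if so, how criterion 1 applies to it.

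The cost is an edit to the endpoint text and the charter. Revascularizations are already adjudicated, so the change needs no extra patients and leaves the primary analysis as it is. It should be made before adjudication of these events begins or, if some have already been adjudicated, those cases should be re-read blinded under the revised wording.
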